9.5 Monitoring of adverse events

All events must be controlled and reported in accordance with all applicable regulations and included in the final clinical study report. All physical/clinical symptoms described at each

visit will be recorded as an adverse event if they occur or worsen during the study and are considered to be related to the study drug.

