1.11.2 Safety

Given the severity of the disease COVID-19, there is no study pre-specifying criteria for interrupting follow-up. The protocol team will review blind AE/SAE data every 2 weeks. If there is a worrying number of unexpected AEs, the researcher will request a review of the non-hidden security data in an ad hoc meeting with the external security monitoring committee, which should take place in real time, via videoconference.

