7. MEASURES TO MINIMIZE BIAS: RANDOMIZATION AND BLINDING

An electronically generated randomization list was prepared by an independent statistician, with 110 blocks of 4 participants per block. This randomization list was generated on R software (Package 'blockrand'). The list will be accessible only to non-blinded pharmacists in the study, in an attempt to minimize observation bias. Participants will be randomized by the study pharmacist to their designated treatment regimen at the time of inclusion and will be subsequently identified throughout the study only by their allocated study number, always assigned following chronological order. In case of SAEs, unmasking will be available to DSMB members, and preliminary analyses will be performed even before the scheduled interim analyses, in order to guide early halting of any of the CQ arms. The randomization and blinding procedure will be described in a specific SOP.

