9.6 Adverse Event (AE) and Serious Adverse Event (SAE) definitions

An AE is any unwanted medical occurrence in a patient or clinical study participant who is administered a pharmaceutical product, and this occurrence does not necessarily have to be causally related to treatment. A priori, the efficacy outcomes specified in the protocol will not be considered as AEs, unless, due to the evolution, severity or any other characteristics of these events, the Investigator, in his clinical judgment, considers them exceptional for the situation in question. A Severe AE is any unwanted medical occurrence that, in any dose:

- 1. Result in death or endangers life;
- 2. Demand the patient's hospitalization or the extending of an existing hospitalization;
- 3. Results in disability or significant/persistent incapacity;
- 4. Birth defect or congenital anomaly;
- 5. Constitutes a clinically important event.

Based on a medical and scientific analysis, any other situations in which an urgent report would be appropriate, such as important medical events that may not immediately threaten life or result in death or hospitalization, but that may leave the patient vulnerable or require intervention to avoid one of the other results listed in the definition above.

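### Section 9.5 records symptoms as adverse events only if judged drug-related, against the definition in 9.6, and 9.6 leaves open whether a death attributed to COVID-19 reaches the SAE-triggered DSMB review

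*Protocol*

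**What the plan says.** **What is recorded.** Protocol 9.5 opens broadly: "All events must be controlled and reported in accordance with all applicable regulations and included in the final clinical study report". Its next sentence sets the working rule for each visit: physical or clinical symptoms become adverse events "if they occur or worsen during the study and are considered to be related to the study drug". Section 9.6 defines an AE the other way: "this occurrence does not necessarily have to be causally related to treatment".

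**Where deaths go.** Section 9.6 states that, a priori, "the efficacy outcomes specified in the protocol will not be considered as AEs, unless" their course, severity or other features are such that "the Investigator, in his clinical judgment, considers them exceptional for the situation in question". The same section puts death or danger to life first in its list of seriousness criteria. Section 1.5 makes mortality by day 28 the primary outcome.

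**What depends on these records.** Section 1.4.2 lists cumulative incidence of AEs and of grade 3 and 4 SAEs among the secondary objectives, and 1.5 lists the matching outcomes. Section 7 ties early action to SAEs: "In case of SAEs, unmasking will be available to DSMB members", with analyses ahead of the scheduled looks. Section 1.11.2 has the protocol team review blinded AE/SAE data every two weeks. Section 8.1.2 says that no stopping rules are pre-specified.

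**The concern.** The trial compares a higher with a lower dose of the same drug, so AE and SAE incidence by arm is a central description of what the higher dose costs. In severe respiratory disease many symptoms have a ready explanation in the illness, and a blinded assessor has no independent means of separating the two. The protocol also encourages attribution away from the drug: 2.3.1.1 says that the listed toxicities have rarely been linked to short use. A symptom never entered as an AE cannot be recovered by any later analysis plan.

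The second part concerns timing. The unscheduled safety reviews in section 7 and section 1.11.2 run on AE and SAE records. If the most serious event in the trial can sit outside those records by default, the reviews may start later than intended, or on an incomplete picture.

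**Working it through.** The contradiction rests on wording, so the texts are traced first. The arithmetic only bounds what can be said about size.

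**1. A symptom blamed on the illness.** Take a new symptom on day 4 that the investigator attributes to pneumonia.
- By the 9.6 definition it is an AE, because causality is not required.
- By the 9.5 recording rule it is not recorded as an AE, because it is not considered drug-related.
- The opening sentence of 9.5 does not settle this. It says that all events are reported, but the next sentence decides which symptoms count as events.

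Sites can therefore capture different data while each follows the protocol.

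**2. A death attributed to COVID-19.**
- Death by day 28 is the primary outcome (1.5), so the carve-out in 9.6 applies by default.
- The exception needs the investigator to find the event exceptional, and no criteria are given. In a population planned at 20% lethality, a death blamed on the disease will not obviously qualify.
- The seriousness list in 9.6 names death, but nothing says whether it overrides the carve-out.
- Whether the death opens the section 7 route, or appears in the 1.11.2 review, is therefore undetermined.

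**3. How many deaths have this status.** Inputs from 5.1: 20% lethality at the low dose, a 50% relative reduction (so 10% at the high dose), 197 per group, 440 in total after 10% losses.
- The plan's own figure is reproduced with unpooled variance: (1.96 + 0.8416)² × (0.20 × 0.80 + 0.10 × 0.90) / 0.10² = 196.2, so 197 per group and 394 in all.
- Expected deaths with 220 per arm: 220 × 0.20 + 220 × 0.10 = 44 + 22 = 66.
- With 197 per arm: 39.4 + 19.7 = 59.1.

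These are upper bounds on the deaths left unsettled. Some may be declared exceptional or recorded as drug-related.

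**4. What the relatedness filter does to the comparison.** The protocol gives no AE rates and no share judged related. As an assumption, take true AE risks of 20% (low dose) and 30% (high dose), 220 per arm, two-sided alpha of 5%, and power = Φ[(|p₁ − p₂| − 1.96·√(2p̄(1 − p̄)/n)) / √((p₁(1 − p₁) + p₂(1 − p₂))/n)].

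| Assumed attribution | Recorded risks | Recorded events | Difference | Power |
|---|---|---|---|---|
| All events recorded | 20% vs 30% | 44 vs 66 | 10 points | 68% |
| 80% of all events judged related | 16% vs 24% | 35 vs 53 | 8 points | 56% |
| 50% of all events judged related | 10% vs 15% | 22 vs 33 | 5 points | 35% |
| 25% of all events judged related | 5% vs 7.5% | 11 vs 16.5 | 2.5 points | 19% |
| 50% of background events, all of the excess | 10% vs 20% | 22 vs 44 | 10 points | 84% |

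The recorded incidence is too low in every filtered row. The difference between doses may shrink or stay the same, and power may fall or rise. Only the undercount has a known direction.

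**The case against.** Much can be said for the protocol, and several stronger readings fail against its text.

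- **That deaths are removed from the safety comparison.** A reader might infer this from "the efficacy outcomes specified in the protocol will not be considered as AEs", but the sentence continues with an investigator exception, and 9.6 names death as a seriousness criterion. Deaths are also counted whatever their AE status. Mortality is the primary outcome, date and cause of death are to be recorded (1.5), 10.1 sets each arm's death proportion against a historical one as a safety measure, and 10.2 tests mortality between arms at three interim looks. This stands. The gap concerns the AE/SAE tables and the reviews that run on them.
- **That a drug-induced death bypasses the SAE route.** A fatal event recognised as drug-related passes the 9.5 filter and meets the first seriousness criterion. The open case is a death attributed to the illness.
- **That arrhythmia, renal or hepatic events never enter the database.** Table 1 schedules a 12-lead ECG on every listed day. Creatinine, bilirubin, ALT and AST over time are a secondary objective, and 9.2 follows laboratory abnormalities without a relatedness condition. The 9.5 filter is worded for physical and clinical symptoms only. This also stands.
- **That escalation depends only on "If there is a worrying number of unexpected AEs".** That wording belongs to 1.11.2. Section 7 offers unmasking in case of SAEs, 8.1.2 promises frequent analyses, and 10.2 allows further safety analyses for the DSMB. The two-weekly review is one route among several.
- **That a particular loss of power follows.** The table above shows that this depends wholly on the assumed attribution pattern, and AE incidence is not the endpoint for which the trial was sized.

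None of this removes the conflict between 9.5 and 9.6 on causality, or says which part of 9.6 governs a death. The interim looks do not fill the second gap either. They come at fixed enrolment fractions, and their lower limit is a futility limit that may be ignored.

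**Conclusion.** The point holds in a limited form. Sections 9.5 and 9.6 contradict each other on whether causality is needed for an AE. If 9.5 is followed, symptom AEs attributed to the illness are undercounted and the comparison of AE/SAE incidence between doses is distorted. The protocol does not allow the amount, or the effect on power, to be calculated.

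Separately, 9.6 does not say whether a death attributed to COVID-19 is an SAE, so it is unclear whether such a death activates section 7 or appears in the two-weekly review. This affects at most about 66 deaths with 220 per arm, assuming the planning rates of 20% and 10%. Those deaths remain in the primary analysis, the interim tests and the 10.1 safety comparison.

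The two sections should be reconciled before enrolment, because what is not recorded at the bedside may not be recoverable.

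**What to change.** 1. **Section 9.5:** record every AE that starts or worsens during the study, whatever its presumed cause, and enter relatedness to study drug as a separate field. AE tables can then be shown both for all events and for related events.
2. **Sections 9.6 and 7:** state that all deaths are included in the SAE tables and in the by-arm data supplied to the DSMB. They may remain exempt from expedited reporting. Say expressly how this statement relates to the carve-out for efficacy outcomes, so that the section 7 route no longer turns on an undefined judgement of what is exceptional.
3. **Section 1.11.2:** make the definition of AE/SAE data match, so that the two-weekly review includes deaths.

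The cost is a wording amendment, one CRF field and somewhat more AE entry. Table 1 already schedules AE recording and clinical evaluation at every visit, so no new assessments are needed. Sample size and interim boundaries are unchanged.

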9.6 Adverse Event (AE) and Serious Adverse Event (SAE) definitions

An AE is any unwanted medical occurrence in a patient or clinical study participant who is administered a pharmaceutical product, and this occurrence does not necessarily have to be causally related to treatment. A priori, the efficacy outcomes specified in the protocol will not be considered as AEs, unless, due to the evolution, severity or any other characteristics of these events, the Investigator, in his clinical judgment, considers them exceptional for the situation in question. A Severe AE is any unwanted medical occurrence that, in any dose:

- 1. Result in death or endangers life;
- 2. Demand the patient's hospitalization or the extending of an existing hospitalization;
- 3. Results in disability or significant/persistent incapacity;
- 4. Birth defect or congenital anomaly;
- 5. Constitutes a clinically important event.

Based on a medical and scientific analysis, any other situations in which an urgent report would be appropriate, such as important medical events that may not immediately threaten life or result in death or hospitalization, but that may leave the patient vulnerable or require intervention to avoid one of the other results listed in the definition above.

10. STATISTICS

10.1 Analytical plan

Descriptive statistics will be used for demographic, laboratory and clinical data. To assess the safety of the high and the low dosages of CQ the proportion (95% CI) of deaths in each group will be compared with the historical proportion (95% CI) of deaths in patients who did not use CQ in other countries. For qualitative variables, Chi-square tests and Fisher's exact test will be performed. t-test or Mann-Whitney test will be used for means/median comparisons. An cumulative proportion of deaths will be assessed by survival models, using Kaplan-Meier estimate curves. Log-rank and Peto-Peto (correction for low observation numbers in the end of the follow-up) tests will be used for survival time to event analyses.

Statistical analyses will be performed in the R statistical package (v3.6.1), and p<0.05 will be considered significant.

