1.2 Study design

This is a randomized, double-blind, placebo-controlled clinical trial. A total of 440 individuals aged between 18 and 80 years, diagnosed with severe respiratory disease, hospitalized in one of the hospitals participating in the study, with suspected SARS-CoV2, will be randomized into two treatment groups at a 1:1 ratio, with group 1 receiving CQ 600mg twice a day for 10 days and group 2 receiving CQ 450mg twice a day on the first day and 450mg once a day for the next 4 days. In order to blind study team and participants, placebo tablets will be used to standardize group 2 treatment for 10 days as group 1. According to the Contingency Plan for coping with Covid-19 in Amazonas, the Hospital e Pronto Socorro Delphina Rinaldi Abdel Aziz Hospital (HPSDRAA), in the north of Manaus, is the reference unit for the admission of serious cases of the new virus. The unit currently has 50 ICU beds, which can increase to a

capacity of 150 ICU beds, 335 beds in total. The hospital also has trained multiprofessional human resources and adequate infrastructure to serve this population. It is the largest hospital in the country dedicated exclusively to the admission of patients with COVID-19, and is publically-privately managed.

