1.3 Sample calculation

The sample for the primary outcome (reduction in lethality) was calculated assuming a 20% lethality incidence in critically ill patients not using CQ (historical control) and that both arms of CQ would be equally able to reduce lethality by at least 50%. Thus, considering a test of differences in proportions between 2 groups of the same size, 80% power and 5% alpha, 394 participants were needed (197 per group). Adding 10% of losses, the final sample of 440 participants was obtained. Sample calculation was performed in the R statistical package (v3.6.1), with the functions implemented in the TrialSize and gsDesign packages.

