1.13 Study flowchart

The therapeutic schematic and mortality assessments are shown in figure 1.

Figure 1. Therapeutic scheme for monitoring patients using chloroquine in lower and higher doses.

Dosage:

| Group 1 (higher dosage – 10 days) | | | | | | | | |
|-----------------------------------|-------------------------------------|------------------------------|--|--|--|--|--|--|
| | 1 st daily dose | 2 ^a daily dose | | | | | | |
| D1 – D10 | 4 tablets of 150mg (600mg) | 4 tablets of 150mg (600mg) | | | | | | |
| | | | | | | | | |
| Group 2 (lowe | r dosage – 5 days CQ + 5 days place | ebo) | | | | | | |
| D1 (Loading | 3 tablets of 150mg (450mg) + | 3 tablets of 150mg (450mg) + | | | | | | |
| dose) | 1 tablets of placebo | 1 tablets of placebo | | | | | | |
| D2 – D5 | 3 tablets of 150mg + | 4 tablets of placebo | | | | | | |
| D2 - D3 | 1 tablets of placebo | 4 tablets of placebo | | | | | | |
| D6 – D10 | 4 tablets of placebo | 4 tablets of placebo | | | | | | |

Administration: Oral (or via nasogastric tube in case of orotracheal intubation - OTI)

Placebo: pills without active ingredient but with the same appearance (there will be no exclusive placebo arm) will be used to standardize treatment.

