3. OBJECTIVES AND OUTCOMES

The general objective of the study is to evaluate the clinical efficacy, safety of therapy and reduction of mortality in hospitalized adult patients with severe respiratory syndrome using two different dosages of chloroquine. Objectives and outcomes are shown in table 2.

 Table 2: Objectives and outcomes.

| Objectives | Outcomes | | | | | | |
|--|---|--|--|--|--|--|--|
| Primary | | | | | | | |
| To assess whether the therapeutic regimen of | Reduction of mortality by 50% | | | | | | |
| Group 1 reduces mortality by 50% in the study | | | | | | | |
| population compared to Group 2. | | | | | | | |
| Secondary | | | | | | | |
| - Assess mortality on days 7, 14 and 28 after | - Mortality on days 7 and 14 | | | | | | |
| hospitalization; | - Clinical status of the subject on days 14 | | | | | | |
| - Assess clinical improvement (use of | and 28 | | | | | | |
| supplemental oxygen, ICU stay, length of stay | -Daily clinical status during | | | | | | |
| in the ICU, length of hospital stay, need for OTI | hospitalization | | | | | | |
| and time on mechanical ventilation, radiological | - Need for and duration of supplementary | | | | | | |
| alterations and time taken to improve the | oxygen | | | | | | |
| radiological and resonance pattern); | - Need for and duration of mechanical | | | | | | |
| - Assess the percentage of SARS-CoV2 | ventilation | | | | | | |
| detection in OPS and blood samples on days 1, | - Length of hospitalization | | | | | | |
| 3, 5, 7, 14 and 28 in the study population; | - Data and cause of death (if applicable) | | | | | | |
| Quantify the SARS-CoV2 virus in | - Prevalence of grade 3 and 4 adverse | | | | | | |
| oropharyngeal swab, nasal swab, OPS and blood | events; | | | | | | |
| samples on days 1, 3, 5, 7, 14 and 28 in the study | - Prevalence of serious adverse events; | | | | | | |
| population; | - Leukogram, hemoglobin, platelets, | | | | | | |
| - Alterations in white cell count, hemoglobin, | creatinine, CK, glucose, total bilirubin, | | | | | | |
| platelets, creatinine, glucose, total bilirubin, | ALT and AST on days 1, 3, 5, 7 (while | | | | | | |
| ALT and AST over time. | hospitalized); and on days 14 and 28 (if | | | | | | |
| - Cumulative incidence of serious adverse | patient is able to return to the clinic or is | | | | | | |
| events (SAEs); | still hospitalized); | | | | | | |
| - Cumulative incidence of grade 3 and 4 adverse | - Negative presence of the virus in | | | | | | |

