4.2 Scientific basis for the study design

Currently, there is no specific antiviral therapy for coronavirus infections. Few treatment studies have been conducted because most strains of human coronavirus cause self-limiting diseases and care is of a supportive nature. After the severe acute respiratory syndrome (SARS), the coronavirus was identified in 2002 and caused a major global outbreak, there has been a growing interest in the development of specific therapeutic agents. Since the SARS outbreak, new therapeutic agents which target the entry of viral proteins, proteases, polymerases and methyltransferases have been tested, however, none of them have been shown

to be effective in clinical trials. Thus, in the absence of a known effective therapy, the situation of a global public health emergency and evidence regarding the potential chloroquine inhibitor (CQ) in most coronaviruses, including SARS-CoV1 and others of a clinical nature, we intend to investigate the efficacy and the safety of CQ diphosphate in the treatment of hospitalized patients with severe respiratory syndrome due to SARS-CoV2. Preliminary trials of CQ repositioning in the treatment of COVID-19 have been encouraging.

This study uses an adaptable design that assesses a safe and effective therapeutic agent (chloroquine) for COVID-19 during the pandemic. The research product (chloroquine diphosphate) is easy to obtain, since it is produced on a large scale within the national territory and is widely distributed to all states by the National Malaria Program, of the Brazilian Ministry of Health. In addition, as the cases have increased, the low cost of chloroquine diphosphate and the free distribution by SUS is a great benefit. Randomization and blinding are essential to establish the effectiveness of chloroquine. In addition, by collecting clinical and virological data from enrolled patients using a standardized timeline and appropriate data collection instruments, we will also be able to provide valuable information about the clinical course and morbidities associated with severe COVID-19 in a diverse group of adult patients.

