10.2 Sample calculation and interim analysis

The sample for the primary outcome (reduction in lethality in patients with severe respiratory virus treated with a high dosage of chloroquine compared to a low dosage) was calculated based on the following assumptions:

- 3. The 20% lethality incidence in critically ill patients per year in the low dosage group;
- 4. High dosage chloroquine will be able to reduce lethality by at least 50% compared to low dosage chloroquine;

Thus, considering a test of differences in proportions between 2 groups of the same size, with power of 80% and alpha of 5%, 394 participants will be needed (197 per group). Considering 10% losses, the sample size is 440 participants.

To include interim analyses, we recalculate the sample sizes required in each of the analyzes and in the final analysis, using an alpha-spending function approach, in which the type 1 error is controlled by alpha correction final, based on the alphas used for interim analyses. There are several alpha spending functions and there is always a trade-off between how much will be 'spent' on the interim analysis and the final sample size required. In summary, the more difficult it is to reject the null hypothesis in the interim analysis, the less alpha will be spent and the impact will not be large. We will use Hwang-Shih-DeCani spending functions with $\gamma = -4$ for the upper limit (that is, to interrupt the study that rejects the null hypothesis in the interim analysis), which corresponds to a conservative method, equivalent to the upper limit of O 'Brien-Fleming, with little impact on the final sample size. We will also include a lower limit for testing futility, also using the Hwang-Shih-DeCani spending function, but with a less stringent $\gamma = -2$ parameter for a beta spending function. Although the calculation includes a possible interruption due to futility, this can be ignored, at the discretion of the DSMB (or equivalent) without any impact on the type 1 error.

The table below shows the calculations for the 3 interim analyses and for the final analysis, showing both the sample size required in each analysis as well as the upper (one-tailed 2.5%) and lower limits.

| | | | Superior Limit | | | |
|------------|---|----|----------------|--------|-----|--------------|
| Sample | | | | | | |
| size | | | | p one- | | |
| percentage | | N | Z | tailed | Z | p one-tailed |
| | | 10 | - | 0.278 | 3.1 | |
| 25% | 8 | | 0.59 7 | 6 | | 0.0008 |

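### The historical-control comparison named for safety in section 10.1 cannot support a conclusion on chloroquine versus no chloroquine, including harm common to both doses

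*Protocol*

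**What the plan says.** Protocol section 10.1 sets out how the safety of the high and low dosages will be assessed: "the proportion (95% CI) of deaths in each group will be compared with the historical proportion (95% CI) of deaths in patients". The historical patients are described only as people "who did not use CQ in other countries". The section gives no source, sample size, population or comparability condition for the historical series, and no margin or decision rule.

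Section 1.2 opens with "This is a randomized, double-blind, placebo-controlled clinical trial", and section 4.1 uses the same label. Both sections then allocate every participant to one of two chloroquine regimens. Section 1.13 confirms that "there will be no exclusive placebo arm", and section 4.3 limits placebo to blinding.

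The stated purpose varies:

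- Section 1.4.1 and Table 2 set the primary objective as group 1 against group 2 on mortality, and sections 5.1 and 10.2 size the trial for that contrast.
- Section 2.1 presents the trial as an evaluation of the therapeutic effect of chloroquine itself.
- Section 4.2 says "Randomization and blinding are essential to establish the effectiveness of chloroquine".

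The 20% mortality figure has two roles. Section 1.3 sizes the trial "assuming a 20% lethality incidence in critically ill patients not using CQ (historical control) and that both arms of CQ would be equally able"; the effect credited to both arms is a halving of deaths or more. Section 10.2 takes "The 20% lethality incidence in critically ill patients per year in the low dosage group" and has the high dose halve it.

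**The concern.** A comparison of each arm with an outside series cannot separate the effect of the drug from differences in patients, care or calendar time. Here such differences are likely. Patients enter on clinical suspicion with diagnosis made afterwards (schedule footnotes, section 1.12). They are selected by bedside severity criteria (section 5.2). Section 1.10 says their management is dynamic and follows changing Ministry of Health recommendations. Nothing in section 10.1 makes the foreign series comparable on any of these.

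At stake is any statement about chloroquine against no chloroquine. If both doses raise mortality to a similar extent, the randomised contrast is near zero and shows nothing. The historical comparison is then the only mortality analysis that could show it. A local baseline below the foreign figure can hide that harm or make it look like benefit. A local baseline above it can make an inert drug look toxic.

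**Working it through.** **1. The plan's own sample size.** Inputs from section 10.2: 20% versus 10%, power 80%, alpha 5% (taken as two-sided), 1:1 allocation.

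n per arm = (1.960 + 0.842)² × (0.20×0.80 + 0.10×0.90) / (0.20 − 0.10)² = 7.85 × 0.25 / 0.01 ≈ 196.2, so 197 per arm and 394 in total. This matches the protocol. With 10% losses, 394/0.9 = 438, close to the stated 440. With 197 per arm, the power for 20% versus 10% is about 80% in either direction. The high-versus-low question is therefore answerable.

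**2. What the randomised contrast cannot show.** If both arms have the same true mortality, the true difference is zero and the two-sided test rejects with probability 5%, whatever mortality would have been without chloroquine. The assumption in section 1.3 (both arms equally effective, 10% and 10%) is exactly this case. It contradicts sections 5.1 and 10.2.

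**3. Operating characteristics of the historical comparison.** Assumptions, because section 10.1 gives none of these:

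- 197 evaluable patients per arm;
- the historical value is the 20% of section 1.3, taken as fixed;
- harm is flagged if the arm's exact (Clopper-Pearson) 95% CI lies wholly above 20%, and the arm looks protective if it lies wholly below.

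The lower limit first exceeds 20% at 52 deaths (52/197 = 26.4%). The upper limit is below 20% at 28 deaths or fewer (28/197 = 14.2%). With X binomial(197, p), the results are P(X ≥ 52) and P(X ≤ 28):

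| Local mortality without chloroquine (assumed) | Mortality on drug, p | Harm flagged | CI wholly below 20% | Reading |
|---|---|---|---|---|
| 10% | 15% | <0.1% | 43% | real harm missed, often looks protective |
| 20% | 30% | 88% | <0.1% | real harm found |
| 30% | 30% (inert) | 88% | <0.1% | false alarm |

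With Wilson intervals the threshold is 51 deaths, and the 88% entries become 91%. The other entries do not change materially. The second and third rows give the same probabilities because the analysis sees only p. It cannot tell a harmful drug in a 20% population from an inert drug in a 30% population.

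**4. Allowing for uncertainty in the historical figure.** Section 10.1 gives the historical proportion a 95% CI too. If the arm's interval must clear that interval, the chance of flagging p = 30% depends on the unstated size of the historical series (20% deaths assumed):

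| Historical n (assumed) | Harm flagged at p = 30% |
|---|---|
| 100 | 4% |
| 200 | 20% |
| 500 | 47% |
| 1000 | 65% |

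**The case against.** The strongest reply is that the trial does not rest on this comparison. The primary objective is high versus low dose, and the randomised test of deaths is run at three interim looks and at the end. Section 9.2 assesses safety from adverse events, laboratory values and vital signs. Section 7 gives the monitoring committee unmasking and early analyses so that either arm can be halted. Sections 1.2, 1.13 and 4.3 make the role of placebo plain to anyone who reads on, and no analysis depends on the label. The source and size of the historical series could sit in an analysis plan that is not shown.

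Most of this stands, and it rules out three stronger readings.

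- A reader might infer that the efficacy objective cannot be answered. The primary objective can. The general objective in section 3 begins "The general objective of the study is to evaluate the clinical efficacy, safety of therapy and reduction of mortality", but the sentence goes on to refer to two different dosages.
- A reader might infer that a harmful dose could be declared safe. Section 10.1 only says that proportions will be compared. It states no rule for such a declaration, and the flag rule above is an assumption.
- A reader might infer that a doubling of deaths at the high dose would go unseen. The historical comparison would miss it: at a true 20% it flags harm in only about 2–3% of trials. The randomised comparison detects 10% versus 20% with about 80% power.

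The reply does not reach mortality relative to no chloroquine. The interim boundaries in section 10.2 concern rejection of the null and futility between arms, and section 8.1.2 sets no stopping rules. Section 9.5 records symptoms as adverse events only if considered drug-related. Section 9.6 by default keeps efficacy outcomes out of the adverse events. A fuller description of the historical series would improve reporting but would not make the comparison randomised.

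**Conclusion.** The point holds in a limited form. Section 10.1 assigns the mortality-safety assessment of each dose to a non-randomised comparison with an unsourced foreign proportion. No conclusion on safety or efficacy against no chloroquine, including harm common to both doses, can be drawn from it. The between-arm question is unaffected.

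The illustrated size runs from under 0.1% detection of a real rise (10% to 15%) to an 88–91% false alarm for an inert drug at a 30% baseline. Correct detection is also 88–91% when the historical 20% happens to match and mortality rises to 30%. These figures rest on the assumed local mortalities, 197 per arm, a fixed historical 20% and the assumed flag rule. The documents supply only the 20% and the 197. The finding that the answer depends on an unverifiable match of baselines does not depend on the particular values.

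The placebo-controlled label and the wider purpose in sections 2.1 and 4.2 invite the same unsupported conclusion. The two sample-size rationales are inconsistent.

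**What to change.** - **Section 10.1:** name the randomised between-arm difference in deaths (risk difference with 95% CI) as the mortality-safety estimate for dose. Keep the historical proportion as descriptive context, with its source, population and n. State that no conclusion on chloroquine versus no chloroquine will be drawn from it.
- **Sections 1.2, 2.1, 4.1 and 4.2:** describe the trial as a randomised, double-blind comparison of two chloroquine regimens, with placebo for masking only, and bring the stated purpose into line with that.
- **Sections 1.3, 5.1 and 10.2:** reconcile the sample-size rationale, since both arms equally halving a historical 20% and the high dose halving low-dose mortality cannot both be the planning assumption.

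This costs protocol wording only, with no added patients or data. The price is a narrower claim: the trial would report on one regimen against the other and would not offer evidence that chloroquine is safe or effective against no treatment.
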